12.4 Response Criteria

12.4.1 Evaluation of target lesions

Complete Response (CR):	Disappearance of all target lesions
Partial Response (PR):	\geq 30% decrease in the sum of the longest diameter (LD) of target lesions, taking as reference the baseline sum LD
Progressive Disease (PD):	\geq 20% increase in the sum of the LD of target lesions, taking as reference the smallest sum LD recorded since the treatment started or the appearance of one or more new lesions
Stable Disease (SD):	Neither sufficient shrinkage to qualify for PR nor sufficient increase to qualify for PD, taking as reference the smallest sum LD since the treatment started

12.4.2 Evaluation of non-target lesions

Amended: 05/12/15

IRB#: 09-016A(9)

Complete Response (CR):	Disappearance of all non-target lesions
Incomplete Response/ Stable Disease (SD):	Persistence of one or more non-target lesion(s)
Progressive Disease (PD):	Appearance of one or more new lesions and/or unequivocal progression of existing non-target lesions

Although a clear progression of "non-target" lesions only is exceptional, in such circumstances the opinion of the treating physician should prevail, and the progression status should be confirmed at a later time.

12.4.3 Evaluation of best overall response

The best overall response is the best response recorded from the start of the treatment until disease progression/recurrence (taking as reference for progressive disease the smallest measurements recorded since the treatment started). The patient's best response assignment will depend on the achievement of both measurement and confirmation criteria (see section 12.4.1).

Target Lesions	Non-Target Lesions	New Lesions	Overall Response
CR	CR	No	CR
CR	Incomplete response/SD	No	PR
PR	Non-PD	No	PR
SD	Non-PD	No	SD
PD	Any	Yes or No	PD
Any	PD	Yes or No	PD
Any	Any	Yes	PD

Note:

- 1. Patients with a global deterioration of health status requiring discontinuation of treatment without objective evidence of disease progression at that time should be classified as having "symptomatic deterioration." Every effort should be made to document the objective progression, even after discontinuation of treatment.
- 2. In some circumstances, it may be difficult to distinguish residual disease from normal tissue. When the evaluation of complete response depends on this determination, it is recommended

IRB#:09-016A(9)

that the residual lesion be investigated (fine needle aspirate/biopsy) before confirming the complete response status.

12.5 Confirmatory measurement/duration of response

12.5.1 Confirmation

To be assigned a status of PR or CR, changes in tumor measurements must be confirmed by repeat assessments that should be performed no less than 4 weeks after the criteria for response are first met. In the case of SD, follow-up measurements must have met the SD criteria at least once after study entry at a minimum interval of 4 weeks.

12.5.2 Duration of overall response

The duration of overall response is measured from the time measurement criteria are met for CR or PR (whichever is first recorded) until the first date that recurrent or progressive disease is objectively documented (taking as reference for progressive disease the smallest measurements recorded since the treatment started).

The duration of overall CR is measured from the time measurement criteria are first met for CR until the first date that recurrent disease is objectively documented.

12.5.3 Duration of stable disease

Stable disease is measured from the start of the treatment until the criteria for progression are met, taking as reference the smallest measurements recorded since the treatment started.

12.6 Progression-free survival

Progression-free survival (PFS) is defined as the duration of time from start of treatment to time of progression or death from any cause. Patients who are taken off-study because of drug-related toxicity or other adverse event but who are alive and have stable or responding disease at the time of trial discontinuation will be not be censored and will be counted in the survival analyses.

13.0 CRITERIA FOR REMOVAL FROM STUDY

Treatment will continue indefinitely until one of the following criteria apply:

- Disease progression (as determined in Section 12.4.1);
- Intercurrent illness that prevents further drug administration;
- Unacceptable adverse events (as determined in Section 11);
- A treatment delay of >4 consecutive weeks;
- Patient's death;
- Patient's decision to withdraw informed consent;
- Amended: 05/12/15

IRB#:09-016A(9)

- General or specific changes in the patient's condition that renders the patient unsuitable for further treatment;
- Patient becomes pregnant;
- Non-compliance by the patient with protocol requirements;
- Patient is lost to follow-up. If the patient fails to return for follow-up evaluations, every effort should be made to re-establish contact and to determine patient outcome.

14.0 BIOSTATISTICS

This is a single institution, open-label, non-randomized, single-arm phase II evaluation. The primary objective of this study is to determine the 2-month progression free survival (PFS) for patients with advanced or recurrent esophageal and gastroesophageal (GE) junction cancer who are treated with sorafenib 400 mg twice daily. PFS is defined in Section 12.6.

The historical control 2 month PFS for patients with untreated advanced esophageal and GE junction cancer is approximately $50\%^{29}$. Using an exact binomial single stage design we require 35 patients to differentiate between 2-month PFS of 50% and 72% with type I and II error rates of 10% each. If 22 or more patients are alive and progression free at 2 months, the regimen is declared promising. With a total of 35 patients, we also have approximately 89% power to detect an improvement in the response rate from 5% to 18% with a type I error rate of 10%.

If at any time there are 14 or more deaths or progressions before 2 months then the trial will close as it is mathematically impossible to achieve the desired endpoint.

We assume an accrual rate of 1-2 patients per month for a study duration of 18-35 months.

Secondary endpoints involve an assessment of the overall response rate (complete and partial responses), as determined by RECIST criteria. Toxicities will also be assessed and tabulated. While the small sample size precludes any definitive conclusions about differential responses based on the squamous cell carcinoma and adenocarcinoma histologies, any differences observed between the two histologies may be exploratory and hypothesis-generating. Finally, tumor tissue will undergo immunohistochemical staining for phosphorylated extracellular signal-regulated kinase (pERK). Any differential response based on different levels of pERK tumor expression will similarly be hypothesis-generating. Fisher's exact test will be employed to investigate these exploratory analyses.

IRB#:09-016A(9)

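### The only early stop in Section 14 is curtailment at 14 failures; one added futility look would keep N = 35, the 22/35 rule and both 10% error limits at 50% vs 72%, and save about 5 to 6 patients if the true rate is 50%

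*Combined protocol and SAP*

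**What the plan says.** All from Section 14.0 (Biostatistics) unless noted.

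- Null: "The historical control 2 month PFS for patients with untreated advanced esophageal and GE junction cancer is approximately" 50%.
- Design and errors: 35 patients in an exact binomial single stage, to "differentiate between 2-month PFS of 50% and 72% with type I and II error rates of 10% each".
- Decision: "If 22 or more patients are alive and progression free at 2 months, the regimen is declared promising".
- Early stop: "If at any time there are 14 or more deaths or progressions before 2 months then the trial will close", and the reason given is "as it is mathematically impossible to achieve the desired endpoint".
- Accrual: "We assume an accrual rate of 1-2 patients per month for a study duration of 18-35 months".

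No other numerical stop for the trial as a whole is given. Section 13.0 lists reasons to take an individual patient off treatment, and Section 16.2 describes the institution's general monitoring committees. Section 4.2 schedules scans at weeks 4 and 8, each with a window of up to 14 days.

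Sections 1.0 and 4.2 state a different alternative from Section 14: 90% power for 50% against 70%.

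**The concern.** Fourteen failures leave at most 35 − 14 = 21 successes, one short of 22. The stop therefore waits until the result is already settled. The trial would continue, for example, with 13 failures in 20 patients, when all 15 remaining patients would have to succeed. At a true rate of 72% that has probability 0.72^15 = 0.7%. The example is extreme, but it shows how late the rule acts.

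The endpoint is short and accrual is slow, so outcomes arrive while most of the sample is still to be enrolled. If sorafenib does no better than the historical control, about 29 to 30 of the 35 patients are enrolled on average before closure. Section 17.0 lists other options for them (palliative chemotherapy, other studies, supportive care).

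**Working it through.** **Inputs.** From Section 14: n = 35, success at 22 or more, p0 = 0.50, p1 = 0.72, both errors at most 10%, stop at 14 failures, accrual 1–2 per month. From Section 4.2: scans at weeks 4 and 8. Assumed, because the documents do not say: Poisson arrivals, and failures seen either half at week 4 and half at week 8, or all at week 8.

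**Step 1. Reproduce the plan.**
- Type I error: P(Bin(35, 0.50) ≥ 22) = 0.0877.
- Power: P(Bin(35, 0.72) ≥ 22) = 0.9151.
- 35 is the smallest single-stage size meeting both 10% limits, so the stated design reproduces.
- The 14-failure stop changes neither figure, since it closes only trials that have already failed.
- At 70%, the same rule gives P(Bin(35, 0.70) ≥ 22) = 0.865, not the 90% stated in Sections 1.0 and 4.2.

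**Step 2. Add one look, keeping the 22/35 decision.** Close if the first n1 patients include r1 or fewer successes. The probability of declaring the drug promising is

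Σ over x = r1+1 to n1 of P(Bin(n1, p) = x) × P(Bin(35 − n1, p) ≥ 22 − x).

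Eight failures in 15 means r1 = 7; nine failures in 17 means r1 = 8.

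| | Current rule | 8 failures in first 15 | 9 failures in first 17 |
|---|---|---|---|
| Type I error at 50% | 0.0877 | 0.0826 | 0.0842 |
| Power at 72% | 0.9151 | 0.9006 | 0.9063 |
| Power at 70% | 0.865 | 0.847 | 0.854 |
| P(stop at look), 50% | – | 0.500 | 0.500 |
| P(stop at look), 72% | – | 0.034 | 0.026 |
| P(stop at look), 70% | – | 0.050 | 0.040 |

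Both looks stay within the 10% limits at 50% vs 72%. The cost in power at 72% is 91.5 − 90.06 ≈ 1.5 points or 91.5 − 90.6 = 0.9 points. At 70% it is 86.5 − 84.7 = 1.8 or 86.5 − 85.4 = 1.1 points.

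**Step 3. Mean enrolment, by simulation.** The 14-failure stop is kept, accrual is not paused, and the look triggers as soon as the 8th (or 9th) failure among the first 15 (or 17) is seen. Enrolment figures below assume half the failures are seen at week 4.
- True 50%, 15-patient look: 28.9 to 23.0 at 1 per month and 30.0 to 24.1 at 2 per month, a saving of 5.9 in each case. The result is nearly the same if every failure is seen at week 8.
- True 50%, 17-patient look: a saving of about 5.
- True 40%, 15-patient look: 24.7 to 16.9 at 1 per month and 26.0 to 18.2 at 2 per month, a saving of 7.8.
- True 60%, 15-patient look: about 3. True 72%: about 0.5.

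The trigger matters. If the 15-patient look waits for all 15 outcomes while accrual continues, the saving at 50% is only about 4 to 5; if accrual is paused for it, 5.5 to 6.9.

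**Step 4. Is a true rate near or below 50% plausible?** Sections 3.2 and 4.2 put PFS on essentially inactive agents at 1.6 to 2.0 months. If these are medians and PFS is exponential (both assumed), 2-month PFS is 0.5^(2/1.6) = 42% to 0.5^(2/2.0) = 50%. So the range where the look saves most is where the protocol itself places an inactive drug.

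**The case against.** The strongest reply is that nothing here is wrong. Section 14 openly chooses a single-stage design, its figures reproduce, and continuous curtailment already brings mean enrolment at a true 50% down from 35 to about 29–30. That stands. A reader might infer that the late stop is a design error or breaks a promise in the protocol; the documents promise no futility look, so that reading is not supported.

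A reader might also infer that the power to pay for the look is simply spare. It is spare only at 72%. At the 70% stated in Sections 1.0 and 4.2 the current rule already falls short of 90%, and either look moves it further away. The 15-patient look also leaves only 0.06 points above 90% at 72%. Both objections stand.

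Nor is a saving of about 6 general: it belongs to a true rate of 50%. At 60% the 15-patient look lowers the chance of a positive result from 43.6% to 41.8% in return for about 3 patients.

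Early closure would also thin the data for response rate (for which Section 14 claims about 89% power with 35 patients), histology and pERK. At a true 50% the look closes the trial half the time. This is a real cost.

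Finally, the bleeding and perforation warnings in Section 11.4 might be read as an argument for the look. A PFS futility rule does not monitor those events; it only reduces the number of patients exposed to an inactive drug.

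Scan timing is less firm than the simulation assumes: Section 4.2 allows up to 14 days' variation, and Section 12.1 can be read as placing the second scan at week 12. The exact error rates depend only on each patient's 2-month status, but the enrolment savings assume detection at week 4 or 8.

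**Conclusion.** The point holds as a worthwhile, inexpensive improvement to a valid design. Section 14's only early stop is curtailment. One futility look can be added without changing N = 35, the 22/35 decision, the 14-failure stop or compliance with the 10% limits at 50% vs 72%. The error rates are exact. The saving at a true 50% (about 6 patients with the 15-patient look, about 5 with the 17-patient look) is a simulated mean. It rests on 1–2 patients per month, failures seen at week 4 or 8, and closure as soon as the critical failure is seen. It shrinks quickly as the true rate rises. The conclusion about spare power applies to the 72% alternative only.

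**What to change.** First settle the alternative: reconcile the 70% in Sections 1.0 and 4.2 with the 72% in Section 14, and state the power that 22/35 actually has there.

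Then add one sentence to Section 14, for example: 'Accrual stops for futility as soon as 9 of the first 17 patients have died or progressed within 2 months of starting treatment.' The version with 8 of the first 15 saves about one more patient at a true 50% but leaves almost no margin above 90% power. Keep the 14-failure stop and the 22/35 decision. State type I error, power, the chance of stopping at the look, and mean enrolment for the rule chosen, together with the assumed scan timing.

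Cost: 0.9 to 1.5 points of power at 72%, 1.1 to 1.8 points at 70%, and fewer patients for response rate, histology and pERK if the trial closes early. If the team prefers to keep curtailment alone, a sentence in Section 14 saying why would be enough.

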15.0 RESEARCH PARTICIPANT REGISTRATION AND RANDOMIZATION PROCEDURES

15.1 Research participant registration

Confirm eligibility as defined in the section entitled Criteria for Patient/Subject Eligibility.

Obtain informed consent, by following procedures defined in section entitled Informed Consent Procedures.

During the registration process registering individuals will be required to complete a protocol specific Eligibility Checklist.

All participants must be registered through the Protocol Participant Registration (PPR) Office at Memorial Sloan-Kettering Cancer Center. PPR is available Monday through Friday from 8:30am – 5:30pm at [contact]. The PPR fax numbers are [contact] and [contact]. Registrations can be phoned in or faxed. The completed signature page of the written consent/verbal script and a completed Eligibility Checklist must be faxed to PPR.

16.0 DATA MANAGEMENT ISSUES

A Research Study Assistant (RSA) will be assigned to the study. The responsibilities of the RSA include project compliance, data collection, abstraction and entry, data reporting, regulatory monitoring, problem resolution and prioritization, and coordinate the activities of the protocol study team.

The data collected for this study will be entered into a secure database. Source documentation will be available to support the computerized patient record.

16.1 Quality assurance

Weekly registration reports will be generated to monitor patient accruals and completeness of registration data. Routine data quality reports will be generated to assess missing data and inconsistencies. Accrual rates and extent and accuracy of evaluations and follow-up will be monitored periodically throughout the study period and potential problems will be brought to the attention of the study team for discussion and action

Random-sample data quality and protocol compliance audits will be conducted by the study team, at a minimum of two times per year, more frequently if indicated.

16.2 Data and safety monitoring

The Data and Safety Monitoring (DSM) Plans at Memorial Sloan-Kettering Cancer Center were approved by the National Cancer Institute in September 2001. The plans address the new policies set forth by the NCI in the document entitled "Policy of the National Cancer Institute for Data and Safety Monitoring of Clinical Trials" which can be found at: http://cancertrials.nci.nih.gov/researchers/dsm/index.html. The DSM Plans at MSKCC were established and are monitored by the Office of Clinical Research. The MSKCC Data and Safety Monitoring Plans can be found on the MSKCC Intranet at: http://mskweb2.mskcc.org/irb/index.htm.

There are several different mechanisms by which clinical trials are monitored for data, safety and quality. There are institutional processes in place for quality assurance (e.g., protocol monitoring, compliance and data verification audits, therapeutic response, and staff education on clinical research QA) and departmental procedures for quality control, plus there are two institutional committees that are responsible for monitoring the activities of our clinical trials programs. The committees: *Data and Safety Monitoring Committee (DSMC)* for Phase I and II clinical trials, and the *Data and Safety Monitoring Board (DSMB)* for Phase III clinical trials, report to the Center's Research Council and Institutional Review Board.

During the protocol development and review process, each protocol will be assessed for its level of risk and degree of monitoring required. Every type of protocol (e.g., NIH sponsored, in-house sponsored, industrial sponsored, NCI cooperative group, etc.) will be addressed and the monitoring procedures will be established at the time of protocol activation

17.0 PROTECTION OF HUMAN SUBJECTS

Inclusion of women and minorities

MSKCC has filed forms HHS 441 (civil rights), HHS 641 (handicapped individual), HHS 639-A (sex discrimination) and HHS 680 (age discrimination); we also take due notice of the NIH/ADAMHA policy concerning inclusion of women and minorities in clinical research populations. Patients of all races, both males and female, will be enrolled into the protocol. In the New York metropolitan area, there is a high proportion of minority patients (e.g. African-American, Hispanic). In general, about 15% of patients at MSKCC are members of minority ethnic groups. We will actively try to recruit minority patients to this protocol.

Exclusion of children and lactating or pregnant women

Children are excluded from this protocol because there is insufficient data to determine the safety of sorafenib in children. In addition, the incidence of esophageal cancer in children is very low. Similarly, lactating and pregnant women are excluded because of the potential teratogenicity and embryotoxicity of sorafenib.

IRB#: 09-016A(9)

Benefits

It is possible that this treatment will result in shrinkage of tumors or in stabilization of an otherwise progressive disease. It is not known, of course, whether these or any other favorable events will occur. It is not known if this treatment will affect the overall survival of patients.

Costs

The patient will be responsible for the cost of standard medical care, including all drug administration fees and all hospitalizations, even for complications of treatment. Sorafenib will be provided to the patient without charge. Correlative tests will be performed without charge to the patient.

Incentives

No incentives will be offered to patients/subjects to participate in this study.

Alternatives

For patients with metastatic or recurrent esophageal cancer, standard therapy includes standard palliative chemotherapy, radiation or possibly surgery. The patient may also be eligible to participate in other investigational studies. Supportive care is also an option.

Confidentiality

Every effort will be made to maintain patient confidentiality. Research and hospital records are confidential. Patient's name or any other personally identifying information will not be used in reports or publications arising from this study. The Food and Drug Administration or other authorized agencies (e.g. qualified monitors from MSKCC, Bayer Pharmaceuticals) may review patient record and pathology slides, as required. The Investigator should contain Bayer Pharmaceuticals immediately if contacted by a regulatory agency about an inspection at his/her center.

Institutional Review Board

Before study initiation, the Investigator must have written and dated approval/favorable opinion from the IRB for the protocol form, informed consent, patient recruitment materials/process (e.g. advertisements) and any other written information to be provided to patients. The Investigator should also provide the IRB with reports, updates and other information (e.g. Safety Updates, Amendments, Administrative Letters) according to regulatory requirements or institutional procedures. Copies of the initial IRB approval as well as annual re-approvals must be submitted to the study sponsor, Bayer Pharmaceuticals.

IRB#: 09-016A(9)

17.1 Privacy

MSKCC's Privacy Office may allow the use and disclosure of protected health information pursuant to a completed and signed Research Authorization form. The use and disclosure of protected health information will be limited to the individuals described in the Research Authorization form. A Research Authorization form must be completed by the Principal Investigator and approved by the IRB and Privacy Board.

17.2 Serious Adverse Event (SAE) Reporting

Any SAE must be reported to the IRB/PB as soon as possible but no later than 5 calendar days. The IRB/PB requires a Clinical Research Database (CRDB) SAE report be submitted electronically to the SAE Office at [contact] containing the following information:

Fields populated from the CRDB:

- Subject's name (generate the report with only initials if it will be sent outside of MSKCC)
- Medical record number
- Disease/histology (if applicable)
- Protocol number and title

Data needing to be entered:

- The date the adverse event occurred
- The adverse event
- Relationship of the adverse event to the treatment (drug, device, or intervention)
- If the AE was expected
- The severity of the AE
- The intervention
- Detailed text that includes the following information:
 - $\circ~$ A explanation of how the AE was handled
 - A description of the subject's condition
 - o Indication if the subject remains on the study
 - $\circ~$ If an amendment will need to be made to the protocol and/or consent form

The PI's signature and the date it was signed are required on the completed report.

For IND/IDE protocols:

The CRDB AE report should be completed as above and the FDA assigned IND/IDE number written at the top of the report. If appropriate, the report will be forwarded to the FDA by the SAE staff through the IND Office..

IRB#:09-016A(9)

For industrial protocols:

Serious adverse drug-related events should be reported to Bayer/Onyx. In such an event, the investigator should refer to the Pharmacovigilance section of the contract for reporting procedures.

Any safety information exchange between Bayer/Onyx and investigator shall be sent electronically (electronic mailbox) or via facsimile to the attention of the contacts listed below:

Electronic Mailbox:	[contact]
[contact]
Address: Mail only	Global Pharmacovigilance - USA Bayer HealthCare Pharmaceuticals Inc. [name]
Address: FDX or UPS only	[name]

Reports for all Bayer products can also be phoned in to the Clinical Communications Dept:

[contact]

